response. Patients with GST scores higher than 10 ng/ml will not be included in the treatment study, but may be asked to collect a single fecal sample (omnigene and viable).

See Protection of Human Subjects - Recruitment Methods and Consenting Process for detailed information regarding recruitment and consenting.

Experimental Protocol.

mTBI Group (Arm 1)

Before and at completion (month 6) of the rhGH intervention, mTBI subjects will report to the UTMB Institute for Translational Sciences (ITS) Clinical Research Center (CRC) for testing, which will consist of cognitive function assessment (MoCA), determination of brain morphology and connectivity using fMRI, determination of lean mass and fat mass using DEXA, resting energy expenditure, functional testing including leg strength and 6 minute walk test, fatigue measurements, and questionnaires of mood and quality of life, gastrointestinal health, sleep, and food preferences. Blood sampling for measurement of amino acid levels, hormones, and metabolites will be drawn before and 90 minutes (+/- 10 minutes) after a standardized meal. In addition, fecal samples for analysis of the GI microbiome will be collected monthly for the duration of the study. Insulin Growth Factor 1 (IGF-1) levels will be monitored at a month 1 safety visit for all mTBI subjects. The month 1 safety visit will occur +/- 5 days from the expected date based on the baseline study visit. The monthly fecal sampling will occur +/- 7 days from the expected date based on the baseline study visit. The month 6 post study will occur +/- 7 days from the expected date based on the baseline study visit. A member of the study team will contact the subject each month to coordinate fecal sample transport to UTMB, check for adverse events and overall well-being, and ensure compliance and ongoing consent. If a mTBI subject sustains an additional TBI during the study, the study for both the mTBI and household control subject will be extended to collect monthly fecal samples and questionnaires for an additional 6 months. Genotropin will be provided for the additional 6 months.

Household control group (Arm 1)

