analysis of the GI microbiome will be collected monthly for the duration of the study. Insulin Growth Factor 1 (IGF-1) levels will be monitored at a month 1 safety visit for all PASC subjects. The month 1 safety visit will occur +/- 5 days from the expected date based on the baseline study visit. The fecal sampling will occur +/- 7 days from the expected date based on the baseline study visit at months 0, 1, 2, 3, 4, 5, 6, 9 and 12. The month 6 study will occur +/- 7 days from the expected date based on the baseline study visit. The month 9 study will consist of fecal sample and questionnaires only. At month 12, the subject will return to the ITS-CRC to repeat the glucagon stimulation test (GST). Questionnaires and a fecal sample will also be collected at this time. A member of the study team will contact the subject each month to coordinate fecal sample transport to UTMB, check for adverse events and overall well-being, and ensure compliance and ongoing consent. If a PASC subject is infected with COVID again during the study months 9 - 12, the study will be extended to collect fecal samples and questionnaires for an additional 3 months.

Therapeutic Intervention (for mTBI subjects only - Arms 1&2; PASC subjects – Arm 3). Recombinant human growth hormone (rhGH), (GENOTROPIN). Growth hormone (GH) is produced endogenously by the body and is released by the pituitary. Therapeutic rhGH is FDA approved for clinical use for replacement of endogenous growth hormone in children and adults with growth hormone deficiency. GENOTROPIN, the agent to be used in this study is manufactured by Pfizer Inc and contains somatropin, which is a polypeptide hormone of recombinant DNA origin. It contains 191 amino acid residues and is identical to human growth hormone of pituitary origin.

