GENOTROPIN (5 mg) is dispensed in a two-chamber cartridge. The front chamber contains recombinant somatropin (5.8 mg), glycine (2.2 mg), mannitol (1.8 mg), sodium dihydrogen phosphate anhydrous (0.32 mg), and disodium phosphate anhydrous (0.31 mg); the rear chamber contains 0.3% m-Cresol (as a preservative) and mannitol (45 mg) in 1.14 mL water for injection. The reconstituted concentration is 5 mg/ml. GENOTROPIN will be administered utilizing the GENOTROPIN Pen 5 (manufactured by Pfizer, Inc). The GENOTROPIN Pen 5 is a reusable multi-dose pen that the two-chambered cartridge is inserted into. Once the cartridge is inserted into the pen, the two-chambers are mixed. A 31 gauge, ½ inch needle is attached to the pen for administration. The pen can then be dialed on the digital display to the correct dose and administered by the user. The needle is then carefully removed and disposed in a sharps medical waste container provided by the study team. Once the cartridge is empty, a new cartridge can be inserted into the pen, a 5 mg cartridge will last 1 – 2 weeks depending on the dose used. The GENOTROPIN Pen 5 is designed to be easily used, as most GH replacement is for pediatric use. Subjects will undergo a familiarization session with the study team to learn how to load the GENOTROPIN5 cartridges into the GENOTROPIN Pen 5 device, how to dial their dose, and how to administer injections. They will also be given a guide and the web address (<http://www.genotropin.com/genotropin-helpful-tools>) of a video prepared by the makers of GENOTROPIN to take home for reference.

In this study, single injections containing 0.4 mg of GENOTROPIN will be administered to mTBI and PASC subjects on a daily basis until the IGF-1 safety check at month 1. If the IGF-1 value is less than 400 ng/mL, the subject will be directed to increase the dose to 0.6 mg per day for the remainder of the study. 0.6 mg per day is the standard dose given in our TBI research studies. We have treated approximately 60 TBI research subjects over approximately 14 years at this dose without incident. [name] also has approximately 100 patients in his clinic being treated at 0.6

mg per day. At this dose of GH replacement, there is no evidence of insulin resistance and as long as the IGF-1 remains at or below 400 ng/mL, there is minimal risk of carpal tunnel syndrome.

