- Screening Blood Labs. Household controls will have the following labs drawn for screening. Approximately 20 ml of blood will be taken for screening labs listed below. The labs will be sent to the UTMB clinical laboratory for analysis and will be entered into subjects UTMB medical chart:
 - Complete blood count with differential (CBC w/ diff)
 - Comprehensive metabolic panel (CMP)
 - Lipid Panel
 - Thyroid-stimulating hormone (TSH)
 - Hepatitis B surface antigen
 - Hepatitis C virus antibody
 - HIV screen
- History and Physical. Household control subjects will undergo a medical history and physical examination by a study nurse or physician.

Study Procedures for mTBI subjects (Arm 1 & 2) / PASC subjects (Arm 3):

mTBI and PASC subjects will complete all procedures listed below. Differences in procedures between Arm 1, Arm 2 and Arm 3 will be noted.

- Vital signs. Vital signs will be collected at all study visits. This will include height, weight, blood pressure, pulse, respirations, and temperature. Vital signs will be recorded on the appropriate study visit CRF.
- Blood draw. Subjects will have blood drawn at the baseline (month 0), safety check (month 1), post-study (month 6) and final study (month 12 – Arm 3 PASC only) visits. Blood will be drawn using a butterfly needle from a peripheral vein in the arm.

- Baseline Visit (Month 0):

Up to 15 ml of blood (1-serum separator top (5ml); 1-lithium heparin (6ml); 1-K-EDTA (4ml)) will be collected from fasted (at least 10 hours) subjects for analysis of hormones, amino acids and metabolites. In addition, up to 13ml of blood (1-serum separator top (5ml); 1-lithium heparin (6ml)) will be collected after a standardized meal for the analysis of amino acids.

- Safety Check Visit (Month 1):

Approximately 3.5 ml of blood for Insulin-like growth factor 1 (IGF-1) will be collected. Blood will be sent to UTMB clinical laboratory for analysis and documented in the subject's UTMB medical chart.

- Post Visit (Month 6):

Up to 15 ml of blood (1-serum separator top (5ml); 1-lithium heparin (6ml); 1-K-EDTA (4ml)) will be collected from fasted (at least 10 hours) subjects for analysis of hormones, amino acids and metabolites. In addition, up to 13ml of blood (1-serum separator top (5ml); 1-lithium heparin (6ml)) will be collected after a standardized meal for the analysis of amino acids.

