An additional 20 ml of blood will be collected for the following labs to be sent to the UTMB clinical laboratory for analysis (all labs run at UTMB will be documented in the subject's UTMB medical chart):

- Complete blood count with differential (CBC w/ diff)
- Comprehensive metabolic panel (CMP)
- Lipid Panel
- Insulin-like Growth Factor 1 (IGF-1)

- Final Visit (Month 12) – Arm 3 PASC only:

Up to 15 ml of blood (1-serum separator top (5ml); 1-lithium heparin (6ml); 1-K-EDTA (4ml)) will be collected from fasted (at least 10 hours) subjects for analysis of hormones, amino acids and metabolites.

An additional 20 ml of blood will be collected for the following labs to be sent to the UTMB clinical laboratory for analysis (all labs run at UTMB will be documented in the subject's UTMB medical chart):

- Complete blood count with differential (CBC w/ diff)
- Comprehensive metabolic panel (CMP)
- Lipid Panel
- Insulin-like Growth Factor 1 (IGF-1)

- Urine Pregnancy Test. Urine will be collected from female subjects for a urine pregnancy test prior to DEXA scan. Urine pregnancy test will be performed at the UTMB CRC as POCT. Women who are post-menopausal will be exempt from this test.
- Body Composition. Lean body and fat mass will be measured using DEXA (GE iDEXA) in conjunction with published equations (Wang, 1999). The whole-body scan will be divided into the following sub-regions: truncal area, head, right and left arm, and right and left leg. DEXA will be measured at baseline (month 0) and post (month 6).
- Indirect calorimetry for Resting Energy Expenditure (REE). Expired gases will be collected and analyzed for O₂ and CO₂ concentrations for the determination of energy expenditure and substrate oxidation (19) in mTBI patients using the ITS-CRC indirect calorimetry system, Vmax Encore, Carefusion. The subject will be asked to lie down on a bed and the ventilated canopy hood will be placed over their head and shoulders. The room will be darkened and external noises will be eliminated, as much as possible. The subject will be asked to relax and remain awake but as still as possible for the testing period of 30 minutes. REE will be measured at baseline (month 0) and post (month 6).
- Amino Acid Levels. Circulating blood amino acid levels will be measured before (fasting) and 90 minutes (+/- 10 minutes) after a standardized meal. Amino acids in response to a meal will be measured at baseline (month 0) and post (month 6).

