- Recombinant Human Growth Hormone Administration. mTBI and PASC subjects will be asked to inject themselves with growth hormone daily. The starting dose will be 0.4 mg/day beginning at the baseline study and will increase to 0.6 mg/day when instructed by the study team. The dose increase will happen after the month 1 IGF-1 blood draw and the study team reviews the results and instructs the subject to increase their dose to 0.6 mg/day. TBI subjects will administer growth hormone for 6 months. PASC subjects will administer growth hormone for 9 months. If a mTBI subject sustains an additional TBI during the study period, the study will be extended for an additional 6 months. Genotropin will be provided for the additional 6 months at a dose of 0.6 mg/day.
- Glucagon stimulation test. Arm 3 PASC subjects will have a glucagon stimulation test at month 12. After the IV is placed, 3.5 ml of blood will be collected for the baseline (time: 0 minutes) to test for levels of human growth hormone. 1 mg glucagon (for subjects over 90 kg, 1.5 mg glucagon) will be injected IM in the deltoid muscle of the subject. Additional blood samples (3.5 mL) will be collected to test for levels of human growth hormone at time points: 90 minutes, 120 minutes, 150 minutes, and 180 minutes. All blood samples will be sent to UTMB clinical laboratory for analysis and entered into subjects UTMB medical chart.

Study Procedures for household and healthy control subjects.

Household controls will complete the procedures below. Differences in procedures between Arm 1 and Arm 2 will be noted.

- Vital signs. Vital signs will be collected at all study visits. This will include height, weight, blood pressure, pulse, respirations, and temperature. Vital signs will be recorded on the appropriate study visit CRF.
- Blood draw. Subjects will have blood drawn at the baseline (month 0) and post (month 6) visits. Blood will be drawn using a butterfly needle from a peripheral vein in the arm. Subjects will be fasted for at least 10 hours.
 - Baseline Visit (Month 0):
Up to 15 ml of blood (1 serum separator top (5ml); 1 lithium heparin (6ml); 1 K-EDTA (4ml)) will be collected from fasted (at least 10 hours) subjects for analysis of hormones, amino acids and metabolites. In addition, up to 13ml of blood (1 serum separator top (5ml); 1 lithium heparin (6ml)) will be collected after a standardized meal for the analysis of amino acids.
 - Post Visit (Month 6):

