2. Significant heart, liver, kidney, blood or respiratory disease.
3. History of chest pain or coronary heart disease.
4. Uncontrolled Diabetes mellitus.
5. Any history of a recently (12 months) diagnosed cancer other than a skin cancer (excluding melanoma).
6. Current alcohol or drug abuse.
7. Premorbid history of psychiatric disorder.
8. Premorbid history of head trauma.
9. Pregnancy or become pregnant during the trial.
10. Subjects who are deficient in cortisol or thyroid at screening will be excluded until hormone abnormalities have been corrected.
11. Subjects with chronic pain who are being managed with narcotics will be excluded as the effects of central nervous system depressants may interfere with study test results.
12. Subjects with a history of inflammatory bowel disease, Celiac disease or active diverticular disease.
13. Subjects with MRI incompatible devices.
14. Subjects with severe claustrophobia.
15. Other medical condition or medication administration deemed exclusionary by the study investigators.

Household Control Inclusion criteria

1. Ages 18 and up.
2. Lives in same household as paired mTBI subject that meets inclusion/exclusion criteria.
3. Participant is willing and able to give informed consent for participation in the study.

Household Control Exclusion criteria

1. Significant heart, liver, kidney, blood or respiratory disease.
2. Uncontrolled Diabetes mellitus.
3. Any history of a recently (12 months) diagnosed cancer other than a skin cancer (excluding melanoma).
4. Current alcohol or drug abuse.
5. Premorbid history of psychiatric disorder.
6. Premorbid history of head trauma.

7. Pregnancy or become pregnant during the trial.
8. Subjects who are deficient in thyroid at screening will be excluded until thyroid hormone is replaced.
9. Subjects with a history of inflammatory bowel disease, Celiac disease or active diverticular disease.
10. Other medical condition or medication administration deemed exclusionary by the study investigators.

ARM 2:

mTBI Inclusion criteria

1. Male or female with a diagnosis of mild TBI.
2. At least 6-month post-injury.
3. Ages 18 to 70 years.
4. Participant is willing and able to give informed consent for participation in the study.

mTBI Exclusion criteria

1. Unable to walk unassisted.
2. Significant heart, liver, kidney, blood or respiratory disease.
3. History of chest pain or coronary heart disease.
4. Uncontrolled Diabetes mellitus.

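### Low-cost improvement: after dosing starts, pregnancy tests for women on rhGH follow the DEXA schedule, so none is planned at month 1, in PASC treated months 6-9 or in the re-injury extension

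*Combined protocol and SAP*

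**What the plan says.** The exclusion criteria for mTBI subjects in Arms 1 and 2 and for PASC subjects in Arm 3 all contain "Pregnancy or become pregnant during the trial". The second half of that item can be met only after enrolment.

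The screening procedures for mTBI and for PASC include a urine pregnancy test, with post-menopausal women exempt. The Study Procedures section for treated subjects then says "Urine will be collected from female subjects for a urine pregnancy test prior to DEXA scan". The Body Composition item fixes the scan dates: "DEXA will be measured at baseline (month 0) and post (month 6"). Dosing begins at the baseline study, so the month 0 test coincides with the start of rhGH.

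Three later stretches of treatment list no pregnancy test:

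- **Month 1 safety visit.** The Blood draw item says "Approximately 3.5 ml of blood for Insulin-like growth factor 1 (IGF-1) will be collected". The Therapeutic Intervention section adds: "If the IGF-1 value is less than 400 ng/mL, the subject will be directed to increase the dose to 0.6 mg per day".
- **PASC after month 6.** Under Recombinant Human Growth Hormone Administration, "PASC subjects will administer growth hormone for 9 months". The PASC Group (Arm 3) section says "The month 9 study will consist of fecal sample and questionnaires only".
- **Re-injury extension.** The mTBI Group sections for Arms 1 and 2 extend stool sampling and questionnaires after a new TBI, and "Genotropin will be provided for the additional 6 months". The dose there is 0.6 mg/day.

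Staff contact each treated subject monthly about adverse events and well-being. The Data Safety and Monitoring Plan covers laboratory values, medical history, injection reactions and rhGH treatment. Neither place names pregnancy.

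**The concern.** The test is attached to the scan, and the drug is given on a different calendar. A subject can meet the plan's own exclusion while still injecting, and the schedule would not look for it for up to six treated months at a time.

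Month 1 is the clearest missed opportunity. The subject is already at the centre for a safety check, and the result decides whether her dose rises from 0.4 to 0.6 mg/day. In PASC, and in a re-injured mTBI subject, dosing continues after the last scheduled test. What is at stake is whether an exclusion the sponsor already wrote is checked during exposure. No endpoint or analysis is involved.

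**Working it through.** The plan states no figure on this point, so the check sets the test dates beside the dosing windows and then sizes the remedy.

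**Test dates against exposure** (sources: Urine Pregnancy Test, Body Composition and Recombinant Human Growth Hormone Administration items; PASC Group and mTBI Group sections)

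| Group | Months on rhGH | Scheduled tests | Tests after first dose | Treated months after last test |
|---|---|---|---|---|
| mTBI, no re-injury | 0-6 | screening, 0, 6 | 1, at end of treatment | 0 |
| PASC | 0-9 | screening, 0, 6 | 1, at month 6 | 9 - 6 = 3; 3/9 = 33% |
| mTBI, re-injured | 0 to at most 12 | screening, 0, 6 | 1, at month 6 | at most 12 - 6 = 6; 6/12 = 50% |

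The last row is a maximum because the text does not say whether the extra 6 months run from month 6 or from the re-injury. If they run from a re-injury at month r (r up to 6), treatment lasts 6 + r months and r of those follow the month 6 test. At r = 3 that is 3 of 9.

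**Treated women.** Inputs: 63 women among 125 planned subjects (Targeted/Planned Enrollment Table); 50 mTBI and 25 PASC subjects take rhGH, so 75 are treated; Arm 2 controls are matched to Arm 2 mTBI subjects on age and sex (ARM 2, Subjects).

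Under an even spread of the sexes (assumption), 63/125 = 0.504, and 75 x 0.504 = 37.8 women: 25.2 mTBI and 12.6 PASC.

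Without that assumption, let a, b, c and p be the women among Arm 1 mTBI subjects, Arm 1 household controls, Arm 2 mTBI subjects and PASC subjects, each between 0 and 25. Sex matching puts c women among the Arm 2 controls too. Then a + b + 2c + p = 63, and treated women T = a + c + p = 63 - b - c.

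- Minimum: make b + c as large as possible with a + p = 63 - b - 2c not negative. With b = 25, c can reach 19, giving T = 63 - 25 - 19 = 19.
- Maximum: a + p cannot exceed 50, so b + 2c is at least 13 and b + c at least 7. This gives T = 63 - 7 = 56.

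**Monthly questions**, one per treated month: 6 x (a + c) + 9p = 6T + 3p.

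- Even spread: 25.2 x 6 + 12.6 x 9 = 151.2 + 113.4 = 264.6, about 265.
- Minimum: T = 19 and p = 0, so 19 x 6 = 114.
- Maximum: T = 56 and p = 25, so 336 + 75 = 411. It is attained at a = 24, b = 0, c = 7, p = 25.

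These counts are for planned completers, before removing post-menopausal women (share not given) and before adding dropouts or extensions. The plan expects about 4 Arm 1 pairs to drop out, so more than 75 subjects may start rhGH.

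**The case against.** The strongest case against is that most of this is already handled. Women who can be pregnant are tested twice before or at the first dose. Every treated subject is contacted monthly, and a pregnancy may well be reported there. The exclusion already implies that a pregnant subject leaves. The listed rhGH risks do not mention pregnancy, no re-injury rate is given, and the extension may affect very few women. The consent forms are not in the file and the pre-screening sheets are attachments not shown, so either could carry pregnancy instructions.

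All of that stands as a limit on weight. It does not remove the gap: in the protocol text, no test and no pregnancy question is specified between months 0 and 6, or on drug after month 6.

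A reader might infer more than the documents support:

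- That women could start rhGH untested. They could not; the month 0 test covers the start of dosing.
- That the plan has no basis for withdrawing a pregnant subject. It has one in the exclusion criteria; the Stopping Rules simply do not repeat it.
- That contraception or pregnancy advice is absent. The file cannot show that.
- That rhGH harms a pregnancy, or that results would be biased. Nothing in the documents establishes either.
- That treated women could number anywhere from 63 - 50 = 13 to 63, using the enrolment table alone. Those extremes need all 50 controls to be women, or all to be men, which sex matching in Arm 2 rules out.

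**Conclusion.** The point holds as a low-priority, inexpensive improvement in participant safety. After entry to dosing, the schedule checks the pregnancy exclusion once, at month 6. For mTBI women without re-injury that is too late to alter exposure. PASC women have 3 of 9 treated months with no later on-drug test, and re-injured mTBI women at most 6 of 12.

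The conclusion covers the protocol text only. The sizes rest on the planned sex totals, on Arm 2 matching that equalises the number of women in its two groups, and, for the central figures, on an even spread of the sexes. No number of pregnancies is estimated.

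**What to change.** 1. Add the point-of-care urine test to the existing month 1 visit for treated women who are not post-menopausal, with the result known before any dose increase. This is one test per woman: 19 to 56 for the planned completers, about 38 under an even split.
2. At each existing monthly contact while on rhGH, including PASC months 6-9 and any extension, ask these women about pregnancy, and do a urine test if the answer is positive or uncertain. This is about 265 questions (114 to 411). The PASC section promises contact every month, but no stool is due at months 7 and 8; confirm that the contact still takes place then.

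A cross-reference to the pregnancy exclusion in the Stopping Rules is optional tidying. It would make plain that a PASC subject who tests positive at month 6 does not continue for the remaining 3 months.

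Only month 1 gains a scheduled test; the later gaps are covered by the question and a prompted test. No on-site visit is described at months 2-5 or on drug after month 6, so a prompted test there may need an unscheduled visit. In Arm 1, ending a treated subject also ends her household control, as the existing exclusion already implies. No analysis changes.
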